
To assess durability of clinical outcomes after treatment with IMP from Baseline (i.e. first dose^b of IMP) to Study Visit 1 in study participants previously treated with IMP as part of the Phase III ORACLE MS and CLARITY/CLARITY-EXT clinical trials.
	
Tertiary endpoints to be evaluated via retrospective data collection from medical records or at Study Visit 1:
 
 • Proportion of study participants being bedridden^d • Time from first dose^b of IMP to first use of an ambulatory device^d • Time from first dose^b of IMP to first use of a wheelchair^d • Annualized Relapse Rate (ARR) from time of first dose^b of IMP to Study Visit 1, and by 2-year intervals • Time to conversion to Clinically Definite MS (CDMS) (For ORACLE MS study participants only) • Proportion of study participants diagnosed as Secondary Progressive MS (SPMS) without relapses in the 3 months prior to SPMS diagnosis • Proportion of study participants diagnosed as SPMS with relapses in the 3 months prior to SPMS diagnosis • Proportion of study participants diagnosed as Primary Progressive MS (PPMS) (For ORACLE MS study participants only)

Exploratory Objectives	Endpoints (Outcome Measures)

To assess impact on quality of life and cognitive outcomes after treatment with IMP during the period from the last clinical visit in the CLARITY/CLARITY-EXT/ORACLE MS clinical trials to Study Visit 1 in study participants previously treated with IMP as part of the Phase III ORACLE MS and CLARITY/CLARITY-EXT clinical trials.
	
Tertiary endpoints to be evaluated at Study Visit 1:
 
 • Change in EuroQoL-5 Dimension Questionnaire (3 level version) (EQ-5D-3L) • Change in cognition as measured by the following assessments (to be collected for ORACLE MS subjects only in countries where these instruments were used in the CLASSIC MS study): 
 ○ The Brief Visuospatial Memory Test – Revised (BVMT-R) ○ Symbol Digit Modality Test (SDMT)

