9.4 Statistical Analyses

The primary endpoint of this study will be evaluated by determining the percentage and 95% CI of patients using a wheelchair the majority of the time in the 3 months prior to Study Visit 1 or patients bedridden any time prior to Visit 1 (as defined in Section 8.1.1.1) for each Cohort and the appropriate subgroups/subsets as defined above in Section 9.3. Forest plots will also be used to display these results.

In addition, proportions adjusted for participation in previous parent studies, as well as other patient characteristics which are deemed to be prognostic for the primary endpoint will be determined applying a logistic regression model. Variables with multiple levels of discrete values will be modeled as categorical variables, and variables with continuous scales (e.g. age) may be modeled as a continuous covariate or categorized where appropriate.

The secondary endpoint, the proportion of patients with EDSS of 6.0 or higher as determined by EDSS documentation or alternative clinical description in medical records after last IMP from parent study. will be presented together with the corresponding 95% CI for each Cohort and appropriate subgroups/subsets as defined above. The results of the confidence scale of EDSS values will be presented descriptively and may be used to interpret EDSS results.

The clinical and MRI characteristics of study participants will be evaluated descriptively by the subgroup long-term responders for Cohort A.

Tertiary endpoints collected retrospectively or at Study Visit 1 will be analyzed descriptively.

Analyses of the change in EQ-5D-3L and change in cognition from the last clinical visit in the parent studies to Study Visit 1 in study participants previously treated with IMP as part of the parent studies will also be performed according to instrument developer instructions and analyzed descriptively to assess the durability of treatment effect.

Similarly, changes in MRI assessment from the last clinical visit in the parent studies to Study Visit 2 will be analyzed descriptively.

In addition, responder rates in high-disease activity (HDA) patients versus the responder rate in non-HDA patients from the CLARITY/CLARITY-EXT population will be analyzed descriptively.

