
To assess durability of clinical outcomes after treatment with IMP from Baseline (i.e. first dose of IMP) to Study Visit 1 in study participants previously treated with IMP as part of the Phase III ORACLE MS and CLARITY/CLARITY-EXT clinical trials.
	
Tertiary endpoints to be evaluated via retrospective data collection from medical records or at Study Visit 1:
 
 • Proportion of study participants being bedridden^d • Time from first dose^b of IMP to first use of an ambulatory device^d • Time from first dose^b of IMP to first use of a wheelchair^d • Annualized Relapse Rate (ARR) from time of first dose of IMP to Study Visit 1, and by 2-year intervals • Time to conversion to Clinically Definite MS (CDMS) (For ORACLE MS study participants only) • Proportion of study participants diagnosed as Secondary Progressive MS (SPMS) without relapses in the 3 months prior to SPMS diagnosis • Proportion of study participants diagnosed as SPMS with relapses in the 3 months prior to SPMS diagnosis • Proportion of study participants diagnosed as Primary Progressive MS (PPMS) (For ORACLE MS study participants only) 	
Section 14.3.2

To assess impact on quality of life and cognitive outcomes after treatment with IMP during the period from the last clinical visit in the CLARITY/CLARITYEXT/ORACLE MS clinical trials to Study Visit 1 in study participants previously treated with IMP as part of the Phase III ORACLE MS and CLARITY/CLARITY-EXT clinical trials.
	
Tertiary endpoints to be evaluated at Study Visit 1:
 
 • Change in EuroQoL-5 Dimension Questionnaire (3 level version) (EQ-5D-3L) • Change in cognition as measured by the following assessments (to be collected for ORACLE MS subjects only in countries where these instruments were used in the CLASSIC MS study): • The Brief Visuospatial Memory Test – Revised (BVMT-R) • Symbol Digit Modality Test (SDMT) 	
Section 14.3.3

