6.4 Interim Analyses

An interim analysis was planned to publish results when data from 50% (100 is minimum required) patients were available from cohort A (see section 8.1 for definition of Cohort). This data included the primary and selected secondary endpoints (or their components) as well as the EQ-5D-3L analysis (see Section 14 for further details on analyses and appendix 17.1 for outputs provided); pharmacogenetics and MRI were not planned to be included in the interim analysis. Results of the interim analysis have been disseminated per dissemination plan of the study, but no formal study report has been written.

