6.5 Final Analysis

All analyses described in this IAP will be performed after the final database lock (see Section 14

for further details on analyses) and summarized in final study report. Results of the final analysis will be summarized in a formal study report.

7 Changes to the Planned Analyses in the Clinical Study Protocol

There are no changes to the analyses planned per protocol.

8 Analysis Populations and Subgroups

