14.3.3 Quality of Life and cognitive outcomes

EQ-5D-3L:

The EQ-5D-3L consists of two components - the EQ-5D descriptive system and the EQ visual analogue scale (EQ VAS). The descriptive system comprises the following five dimensions:

- Mobility
- self-care
- usual activities
- pain/discomfort
- anxiety/depression

Each dimension has three levels: no problems, some problems, extreme problems (labelled 1–3). The respondent is asked to indicate his health state by checking the box against the most appropriate statement in each of the five dimensions. The EQ-5D descriptive system will be summarized for each dimension as continuous variable at study visit 1.

Respondents indicate their self-rated health on the EQ VAS, numbered from 0 to 100 where the endpoints are labelled “Best imaginable health state” (100) and “Worst imaginable health state” (0). This information can be used as a quantitative measure of health outcome as judged by the individual respondents and will be summarize descriptively at study visit 1.

EQ-5D descriptive system and EQ VAS change from the latest assessment prior to or on first dose of IMP will also be summarized descriptively. In case of missing date in parent study, visit labels (e.g., Screening Visit, Baseline Visit, Unscheduled Baseline Visit) will be used to determine baseline visit.

Computation rule:

If there is no EQ-5D score before or on the first dose of IMP day, then the change will not be calculated.

BVMT-R (Cohort D only):

BVMT-R performance test will be summarized using the following raw scores: “Total recall”, “Delay recall”, “Percent retained (%)” and “Learning Consistency (%)”.

Raw scores at study visit 1 and change from ORACLE MS study latest assessment prior to or on first dose of IMP will be summarized descriptively.

Computation rule:

If there is no BVMT-R score before or on the first dose of IMP day, then the change will not be calculated.

SDMT (Cohort D only):

Total SDMT score (i.e. oral score from sdmt eCRF page) at study visit 1 and change from latest assessment prior to or on first dose of IMP will be summarized descriptively.

Computation rule:

If there is no SDMT score before or on the first dose of IMP day, then the change will not be calculated.

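### EQ-5D and cognition change starts before first dose in SAP 14.3.3 but at the last parent-trial visit in the objective and Protocol 9.4, with no departure declared; the MRI reference and the wheelchair event rule need minor reconciliation

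*SAP*

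**What the plan says.** **(a) EQ-5D-3L, BVMT-R, SDMT.** The objective in Protocol 3 places the assessment "during the period from the last clinical visit in the CLARITY/CLARITY-EXT/ORACLE MS clinical trials to Study Visit 1". SAP 5 repeats it: "during the period from the last clinical visit in the CLARITY/CLARITYEXT/ORACLE MS clinical trials to Study Visit 1". Protocol 9.4 specifies "Analyses of the change in EQ-5D-3L and change in cognition from the last clinical visit in the parent studies to Study Visit 1". SAP 14.3.3, the section to which SAP 5 sends the reader, instead says: "EQ-5D descriptive system and EQ VAS change from the latest assessment prior to or on first dose of IMP will also be summarized descriptively". Its computation rule adds: "If there is no EQ-5D score before or on the first dose of IMP day, then the change will not be calculated". The BVMT-R and SDMT paragraphs use the same starting point and the same rule. SAP 7 says: "There are no changes to the analyses planned per protocol".

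On the interim analysis, SAP 6.4 says: "This data included the primary and selected secondary endpoints (or their components) as well as the EQ-5D-3L analysis". It also says: "Results of the interim analysis have been disseminated per dissemination plan of the study".

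**(b) MRI.** The endpoint in Protocol 3 and SAP 5 takes change from Baseline, defined there as the last scan before first dose. The title of Table 15.2.8.1 also says Baseline. Protocol 9.4 and SAP 14.3.4 start from the final parent-trial visit, which the SAP labels Screening.

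**(c) Wheelchair.** SAP 14.3.2 lists time to first ambulatory device and time to first wheelchair as separate items, and promises Kaplan-Meier curves and estimates covering both. It then gives one event rule: the earliest of wheelchair date, device date, EDSS of at least 6, or death due to MS. Protocol 8.1.1.6 bases first wheelchair use on EDSS 7.0 or higher, or on a clinical description.

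**The concern.** For (a), the two starting points define different quantities. Change from before first dose combines what happened during the parent trial with what happened afterwards. The objective and Protocol 9.4 ask only about the second period. A gain on trial followed by an equal loss after it would appear as no change under SAP 14.3.3 and as a loss under the protocol. A patient with a final-visit score but no pre-dose score gets no change value at all. Because SAP 7 declares no departure, a reader of the study report would have no signal that the reported quantity differs from the protocol's.

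For (b), a programmer following SAP 14.3.4 could fill a table whose title names a different reference scan. For (c), a first cane or an EDSS of 6 ends the clock, so the curve cannot be read as time to wheelchair.

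**Working it through.** **Side by side**

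| Analysis | Objective or endpoint (Protocol 3, SAP 5) | Protocol 9.4 | SAP 14 | Output title (SAP 17.1) |
|---|---|---|---|---|
| EQ-5D, BVMT-R, SDMT | final parent-trial visit (in the objective; the endpoint cell gives no start point) | final parent-trial visit | last score on or before first dose | change, no reference named |
| MRI | last scan before first dose | final parent-trial visit | final parent-trial visit, called Screening | Baseline |
| Wheelchair | own time-to-event endpoint | Kaplan-Meier or cumulative incidence | own item, but only a composite event rule | device/wheelchair combined |

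Only in the first row does the SAP depart from both the objective and Protocol 9.4. In the second row SAP 14.3.4 follows Protocol 9.4, so the conflict starts inside the protocol.

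**What the starting point changes in (a).** For a patient with all three scores:

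change(pre-dose to SV1) = change(pre-dose to last parent visit) + change(last parent visit to SV1).

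SAP 14.3.3 reports the left side. The protocol asks for the last term. They agree only if nothing changed on trial.

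**Distance between the two starting points.** The plan gives no figure to reproduce. Inputs from SAP 6.2: CLARITY 96 weeks; CLARITY-EXT 96 weeks; gap between them median 41 weeks, range 1 day to 118 weeks. SAP 9.4 sets 365.25 days per year. Assumption: an on-schedule completer whose last assessment is at Week 96 of the last parent trial. Years = days / 365.25.

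- CLARITY only: 96 × 7 = 672 days; 672 / 365.25 = 1.84 years.
- CLARITY plus CLARITY-EXT, median gap: (96 + 41 + 96) × 7 = 1631 days = 4.47 years.
- Shortest gap: (96 + 96) × 7 + 1 = 1345 days = 3.68 years.
- Longest gap: (96 + 118 + 96) × 7 = 2170 days = 5.94 years.

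Protocol 9 puts the study visits around 10 years after initial treatment. Against 10 years, these distances are about 18%, 45%, 37% and 59%.

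If assessments were also made at the end of the 24-week safety follow-up after CLARITY-EXT, which neither document confirms, the median-gap figure becomes 257 × 7 = 1799 days = 4.93 years and the longest 334 × 7 = 2338 days = 6.40 years. No figure can be given for ORACLE MS, the only source of BVMT-R and SDMT, because its treatment schedule depended on conversion and the trial ended early.

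**Interim exposure for (a), from SAP 17.1.** Table 15.2.7.1 (quality of life) is marked for the interim. Tables 15.2.7.2 (BVMT-R) and 15.2.7.3 (SDMT) are not. That is one of three.

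**The case against.** **On (a).** The pre-dose score is a defensible reference. SAP 9.3 defines Baseline that way, the neighbouring objective on durability of clinical outcomes runs from first dose, and pre-dose scores may be more complete than final-visit ones. The endpoint cell itself says only that change is measured. All of this stands, and it is why the pre-dose row should be kept. It does not remove the conflict with the paired objective and Protocol 9.4, or the statement in SAP 7.

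**On (b).** Pre-dose scans may not all be usable. SAP 14.3.4 confines the T2 changes to ORACLE MS without giving a reason. That is a fair caution against fixing the reference scan before availability is checked.

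**On (c).** A reader might infer that no wheelchair Kaplan-Meier estimate is planned. The documents do not support this. SAP 14.3.2 promises estimates for both device and wheelchair, from first and from last dose. The output titles do not show the first-dose and last-dose split either, so the lack of a wheelchair-only title proves little. Table 15.2.6.1 may also describe wheelchair use, though its content is not specified. What stands is narrower: the single rule supplied gives no wheelchair event.

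**Conclusion.** Part (a) holds and should be corrected. SAP 14.3.3 computes a different change from the one in the objective and Protocol 9.4, and the SAP says nothing has changed. The starting points lie about 1.8 years apart for CLARITY only and 4.5 years (3.7 to 5.9) for CLARITY plus CLARITY-EXT, under the Week 96 completer assumption. These are calendar distances. They do not measure any effect on an estimate, and the number of patients affected cannot be derived.

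A reader might infer that the disseminated interim EQ-5D result used the wrong definition. The documents do not show which definition was used, so the most that can be asked is that it be stated.

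Parts (b) and (c) are minor reconciliations. A reader might take (b) as a SAP departure from the protocol, but the SAP follows Protocol 9.4. Everything here is tertiary and descriptive; the primary endpoint and the EDSS 6.0 secondary endpoint are unaffected.

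**What to change.** **(a) SAP 14.3.3 and SAP 7.** Make change from the last available parent-study assessment to Study Visit 1 the protocol analysis for all three instruments, and report how many patients have such a score. Keep change from the pre-dose score as a separately labelled row. Record the change in SAP 7, or declare the departure there if final-visit scores do not exist. State which definition the interim used.

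**(b) Protocol 9.4 and SAP 14.3.4.** Check scan availability, then align both with the endpoint's pre-dose Baseline and drop the Screening label. If that is not possible, declare the departure in SAP 7.

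**(c) SAP 14.3.2.** Label the composite as time to ambulatory device or worse. Add a wheelchair event rule following Protocol 8.1.1.6: wheelchair date or EDSS 7.0 or higher. Whether first bedridden date and MS death also count is a choice that the protocol does not settle for this endpoint, and the SAP should state it.

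**Cost.** SAP wording, one protocol sentence, one extra derivation per instrument, one added Kaplan-Meier analysis and a short statement on the interim. SAP 6.3 already brings in the parent-study data, and the wheelchair and bedridden dates are already collected. The one unknown is whether final-visit EQ-5D and cognition scores exist, so that should be checked first.

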14.3.4 Durability of outcomes on brain imaging

Changes in MRI assessment from the last clinical visit in the parent studies (called “Screening”) to Study Visit 2 will be analyzed descriptively for the MRISS analysis population for the following MRI parameters.

- Changes in number of total T2-W Lesions from Screening to Study Visit 2 (only for ORACLE MS)
- Changes in number of total T1-W Lesions from Screening to Study Visit 2
- Percentage changes in volume of total T2-W Lesions from Screening to Study Visit 2 (only for

ORACLE MS)

- Percentage changes in volume of total T1-W Lesions from Screening to Study Visit 2
- Percentage in Brain Volume changes from Screening to Study Visit 2
- Percentage of ventricular Atrophy: Longitudinal from Screening to Study Visit 2

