
To assess durability of outcome on brain imaging after treatment with IMP from Baseline (i.e. the last MRI before first dose of IMP; if feasible, by year) to within 3 months after Study Visit 1 in study participants previously treated with IMP as part of the Phase III ORACLE MS and CLARITY/CLARITY-EXT clinical trials.
	
ORACLE MS, CLARITY and CLARITY-EXT study participants from selected sites will be invited to participate in a follow-up study visit (Study Visit 2) to take place within 3 months (maximum 4 weeks from Visit 1 after last patient enrolled) following Study Visit 1, for evaluation of the following:
 
Change in MRI assessment from Baseline (i.e. the last MRI before first dose^b of IMP) to Study Visit 2 in:
 
 • Total volume of T2 lesions • Total number of T2 lesions • Number of hypointense lesions on T1-spin echo MRI • Volume of hypointense lesions on T1-spin echo MRI • Brain volume or surrogate (in cases where brain volume is not possible to assess for technical reasons, then 3rd ventricle diameter may be evaluated) • Ventricular volume 	
Section 14.3.4

Objectives	Endpoints (Outcome Measures)	IAP section
To determine whether the high-disease activity (HDA) patients from the CLARITY/CLARITY-EXT clinical trials are more likely to be the long-term responders.	Comparison of the responder rate in HDA patients ^c versus the responder rate in non-HDA patients from the CLARITY/CLARITY-EXT population.	Section 14.3.5
To evaluate differences in genetics between long-term responders and study participants requiring alternate therapies following treatment with IMP for the CLARITY/CLARITY-EXT and ORACLE MS populations.	Correlation of genetic variations with long-term responders (defined as study participants who did not demonstrate any evidence of disease reactivation based on Investigator assessment of clinical and imaging outcomes until Year 4 or later following their last dose ^b of IMP and who did not receive disease modifying treatment until Year 4 or later following their last dose ^b of IMP) compared to other study participants who started on alternate therapy less than 4 years following their last dose ^b of IMP for the CLARITY/CLARITYEXT and ORACLE MS populations.	Section 14.3.6

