
Patients should have at least 1 relapse in the previous year while on therapy
	
≥1 relapse in previous year while on therapy. While on therapy is calculated as follows:
 
If duration of DMD treatment is ≥365 days and end date is within 1 year of PSD1, then relapses are considered "while on therapy", if occurring in time period coinciding with DMD therapy.
 
Graphical Representation of Relapse while on therapy
  
Data processing/Handling of partial dates:
 
Relapses with partial onset date are imputed as follows:
 
 • Missing day will be imputed to be 15 and missing month will be imputed to be June. • No imputation for complete missing date. 
Relapses are collected when associated with a date. If no date of relapse is reported, number of relapses is set to 0 (zero).

and have at least 9 T2-lesions
	
≥9 Total T2 lesions prior to first study.
 
Handling of missing data: If T2 lesion is missing prior to first study, subject is considered in the <9 T2 lesions.

or at least 1 Gadolinium-enhancing lesion
	
≥1 T1 Gadolinium-enhancing lesion prior to first study
 
Handling of missing data: If T1 lesion is missing prior to first study, subject is considered in the <1 T1 Gd+ lesion.

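### SAP 14.3.4 restricts T2 lesion change to ORACLE MS, unexplained and undeclared, although the endpoint also covers CLARITY and CLARITY-EXT

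*SAP*

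**What the plan says.** **Population.** The objectives table in SAP section 5, like Protocol section 3, opens the MRI change endpoint with "ORACLE MS, CLARITY and CLARITY-EXT study participants from selected sites will be invited to participate in a follow-up study visit". It then lists T2 volume and number, T1 hypointense lesion number and volume, brain volume and ventricular volume, with no limit by parent study.

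**Analysis.** SAP section 14.3.4 lists "Changes in number of total T2-W Lesions from Screening to Study Visit 2 (only for ORACLE MS" (closing bracket follows). It also lists "Percentage changes in volume of total T2-W Lesions from Screening to Study Visit 2 (only for", where the restriction runs over a page break and again names ORACLE MS. The T1, brain volume and ventricular items carry no such limit. Lesion numbers are analysed as changes. Lesion volumes are analysed only as percentages, for example "Percentage changes in volume of total T1-W Lesions from Screening to Study Visit 2".

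**Reference point.** SAP section 14.3.4 measures "Changes in MRI assessment from the last clinical visit in the parent studies (called “Screening”) to Study Visit 2", and Protocol section 9.4 also uses the last parent-study visit. The endpoint tables in Protocol section 3 and SAP section 5 use the last scan taken before the first dose.

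**Declared departures.** SAP section 7: "There are no changes to the analyses planned per protocol".

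**Output.** In SAP section 17.1, Table 15.2.8.1 reports MRI change for Cohort A, the pool of all parent studies.

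**The concern.** The analysis is narrower than the endpoint it serves, and nothing says why. Where the plan intends an ORACLE-only endpoint (conversion to CDMS, PPMS diagnosis, cognition), the objectives table says so. For T2 change it does not.

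CLARITY and CLARITY-EXT supply the relapsing-remitting patients, while ORACLE MS enrolled patients after a first clinical event. Following the SAP answers the T2 durability question only in first-event patients, in a table labelled as the pooled cohort. A reader of that table could take the T2 rows to describe everyone.

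Three smaller gaps sit in the same MRI plan and need the same repair:

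- two competing reference points;
- no absolute change in lesion volume, and no rule for a zero baseline;
- ventricular volume missing from the Study Visit 2 characteristics in SAP section 14.2.3, although footnote c of SAP section 5 lists it for that secondary endpoint.

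**Working it through.** **1. Which places agree.**

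| Place | T2 change covers |
|---|---|
| Protocol section 3 | ORACLE MS, CLARITY, CLARITY-EXT |
| SAP section 5 | ORACLE MS, CLARITY, CLARITY-EXT |
| Protocol section 9.4 | no restriction |
| SAP section 14.3.4 | ORACLE MS only |
| SAP section 17.1, Table 15.2.8.1 | Cohort A (all studies) |
| SAP section 7 | no departure declared |

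SAP section 14.3.4 stands alone.

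**2. Could CLARITY T2 change be computed?** At follow-up, SAP section 14.2.3 reports T2 number and volume at Study Visit 2 for all cohorts. Before treatment, SAP section 8.2.2 classifies high disease activity in CLARITY patients from parent-study data using "≥9 Total T2 lesions prior to first study". So a pre-study count exists for at least some of them. The same table places missing counts below the threshold, so completeness is not shown. No passage shows a CLARITY T2 volume, or a T2 count at the last parent-study visit, which is the reference that SAP section 14.3.4 uses.

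**3. Size.** Inputs are the parent-study counts in SAP section 6.1 and the approximate MRI sub-study size of 150 in Protocol section 4.1.

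- Check of the stated total: 1326 + 617 = 1943, which reproduces.
- CLARITY share of parent patients: 1326 / 1943 = 68.2%.
- MRI patients without a T2 change result = 150 × CLARITY share of the sub-study. That share is not stated, so a range is assumed:

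| Assumed CLARITY share | Without T2 change | With T2 change |
|---|---|---|
| 50% | 75 | 75 |
| 68.2% (proportional) | 102 | 48 |
| 80% | 120 | 30 |

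**4. Percentage change in volume.** Percentage = 100 × (follow-up − baseline) / baseline. For the same illustrative rise of 0.5 cm³:

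| Baseline (cm³) | Absolute change (cm³) | Percentage change |
|---|---|---|
| 5 | 0.5 | +10% |
| 1 | 0.5 | +50% |
| 0.1 | 0.5 | +500% |
| 0.01 | 0.5 | +5000% |
| 0 | 0.5 | undefined |

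The share of patients with zero baseline volume is not in the documents. Each 10 percentage points of such patients would remove 150 × 0.10 = 15 of 150 from the T1 volume summary.

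**5. Ventricular volume.** Footnote c of SAP section 5 names six Study Visit 2 characteristics. SAP section 14.2.3 lists five: T2 number, T1 number, T2 volume, T1 volume and brain volume. Ventricular volume is the one left out.

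**The case against.** The restriction may have a sound technical cause. Meeting a threshold of 9 lesions, with missing values assigned to the lower class, is a weaker requirement than a complete count that can be compared with a central read about ten years later. This stands. A reader might infer from the high-disease-activity rule that CLARITY T2 change is simply available, but the documents do not support that, least of all for volume.

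Substituting the pre-study count would also create a new problem. SAP section 14.3.4 refers to the last parent-study visit, so one table would mix pre-dose and end-of-study references. This stands too, and it is why the reference point must be settled first.

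On percentages, a reader might infer that the SAP has replaced the endpoint with a different measure. It has not: the endpoint says change without specifying absolute change. SAP section 9.5 already requires medians, quartiles and missing counts, which limit the influence of near-zero baselines. Absolute change in T1 lesion number is reported for all studies, so a patient who goes from none to some still appears in the section. Nor do the documents show that zero T1 volume marks the lowest overall lesion burden, so a claim of bias from losing those patients goes too far. What remains is narrower: an undefined value, no rule for it, and no absolute volume summary.

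Finally, this is a tertiary, descriptive endpoint in an optional sub-study. CLARITY patients keep their T1, brain volume and ventricular change results and their Study Visit 2 T2 values. That lowers the stakes but does not explain the omission.

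**Conclusion.** The point holds as an undeclared and unexplained narrowing of a stated endpoint. Followed as written, the SAP yields no T2 change result for CLARITY or CLARITY-EXT participants, while the table title says Cohort A. At an assumed CLARITY share of 50% to 80%, that is 75 to 120 of about 150 patients. The proportional figure of 102 is only one point in that range, because MRI sites are chosen on technical capability and availability of the original scanner, not in proportion to enrolment.

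A reader might convert the loss into a wider confidence interval for pooled T2 change. The documents do not support such a figure: it would need an assumed split, equal variances and pooling, and the ORACLE MS interval does not change when results are shown by parent study.

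The documents also do not show that the restriction is technically wrong, only that it is neither justified nor declared. The volume-metric gap is real but of unknown size. The ventricular omission is plain from the text and affects a secondary endpoint. None of this touches the primary endpoint, and the SAP should be corrected before the final analysis.

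**What to change.** 1. **Reference point first.** Reconcile the last pre-dose scan (Protocol section 3, SAP section 5) with the last parent-study visit (Protocol section 9.4, SAP section 14.3.4). Use one reference for all studies and all MRI parameters, and drop the Screening label if it does not describe that reference.
2. **T2 change.** Remove the ORACLE MS restriction from both T2 items. Report T2 number and T2 volume change for CLARITY/CLARITY-EXT wherever a usable value exists at the chosen reference, shown by parent study with the number available. If no usable values exist, for number or for volume, state the technical reason in SAP section 7, confine that T2 change conclusion to ORACLE MS, and label Table 15.2.8.1 to match.
3. **Lesion volume.** Report absolute change in cm³ (median and quartiles) beside percentage change, and show how many patients have a zero baseline and therefore no percentage.
4. **Ventricular volume.** Add it to the Study Visit 2 characteristics in SAP section 14.2.3 and to the corresponding tables.

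The cost is SAP wording and programming, plus a check of what the parent-study MRI datasets hold. No new data collection is needed. The main drawback is that CLARITY reference reads and Study Visit 2 reads may come from different readers, which is why results should be shown by parent study and not only pooled.
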